Project Name: The association between serum urea nitrogen to creatinine ratio and the survival in patients with DKD.

No.: v1.2 version Date: June 1, 2020

Study unit: Guangdong Provincial People's Hospital

Sponsor: Guangdong Provincial People's Hospital

Background

In 2013, the prevalence of adult diabetes in China was as high as 10.9%, with the number of patients exceeding 100 million. Diabetic kidney disease (DKD), as one of the main microvascular complications of diabetes, occurs in 20% ~ 40% of diabetes. Furthermore, Diabetes-related chronic kidney disease, the leading cause of chronic kidney disease, has become a serious public health problem and brought huge economic burden. How to realize the early prevention and treatment of DKD and improve its clinical outcomes raises our concerns.

Previous studies have shown that a low-protein diet (LPD) can retard renal function decline in patients with CKD mainly through the improvement of glomerular hyperfiltration/hyperfusion and tubule-interstitial damage, inflammation and fibrosis. The lower the baseline dietary protein intake (DPI), the slower the progression toward ESRD. Each 0.1 g/kg per day higher DPI at baseline was associated with a loss of kidney function that was faster by approximately 0.064 ml/min per year. In 2020, standards of medical care in diabetes of American diabetes Association (ADA) recommended for people with nondialysisdependent CKD to maintain DPI approximately 0.8 g/kg body weight per day. Previous studies provided some methods for dietary assessment such as 24-hour dietary recalls, food diaries and food frequency questionnaires, which exist limitations including:(1)reliance on patient's memory, compliance and communication ability; (2)reliance on interviewer's skills, comprehensiveness and prompts;(3)lack of ability to represent a longer period. Maroni formula, which tests 24-hour urine urea nitrogen, is a relatively objective and common method to evaluate protein intake, but can't be generalized due to its complexity and uncertainty. Joel D et.al found that serum urea nitrogen to creatinine ratio (sUCR) correlated closely with protein intake and knowledge of its relation to protein intake could be used to determine the degree of protein restriction. In our previous study, the mathematical model between sUCR and DPI was preliminarily established after modeling and verification, and has obtained the patent.

Protein restriction is a basic but important life intervention to improve the prognosis of DKD patients. How to calculate DPI in a simple and effective way to overcome the complexities and errors of existing methods attracts our attentions. In this study, we hypothesize sUCR can be applied to evaluate of protein intake during the follow-up periods and predict the survival in patients with DKD.

Object

To evaluate the prognostic value of sUCR in the progression of DKD.

Methods

This study is a multicenter, retrospective cohort study. We select patients diagnosed with DKD since January 2012. The present study is performed according to the principles of the Declaration of Helsinki and has been approved by the Ethics Committee of Guangdong Provincial People's Hospital.

Study population

We screen DKD patients aged 18-70 years with CKD stages 1-4. DKD was defined as those diagnosed by pathological biopsy, or those with eGFR <60 ml/min per 1.73 m², or presence of clinically detectable albuminuria over 3 months which is caused by diabetes. Patients who undergo infection, severe liver disease, malignant tumor, acute heart failure, gastrointestinal hemorrhage, pregnancy are excluded.

Data collection

At baseline and every medical visit, therapeutic relevant information will be collected. Data mainly include demographic characteristics (age, gender, place of residence, marriage status, education degree), lifestyle (smoking, drinking, exercise), clinical characteristics (body mass index, blood pressure, duration, history of CVD, complications, nutrition situation), laboratory indexes (serum creatinine, blood urea nitrogen, glycosylated hemoglobin, urinary albumin to creatinine ratio, 24-hour urinary albumin, 24-hour urine urea nitrogen, etc.). History of cardiovascular disease including coronary artery disease, congestive heart failure, stroke, and peripheral vascular disease were ascertained by self-report or doctor's diagnosis.

Outcomes

Patients are followed for survival until they reach the end of the study, whichever happen first, or are censored because they lose contact or the follow-up interval is less than one month. The outcomes are all-cause death, a composite of end-stage kidney disease (dialysis, transplantation, or a sustained estimated GFR of <15 ml per minute per 1.73 m², or increasing by 50% of the serum creatinine level from baseline. Evaluated GFR was calculated using Chronic Kidney Disease Epidemiology Collaboration (CKD-EPI) formula.

Statistics

Data are presented as mean \pm SD for continuous variables and as a number (percentage) for categorical variables. According to mean sUCR and Δ sUCR (fluctuation of sUCR over time, meaning monthly rate of change), patients are divided into four groups. The relationship between baseline characteristics among the four groups was compared by using one-way analysis of variance test, Kruskal-Wallis test or Chi-squared test where appropriate. Survival rates are estimated using Kaplan Meier analysis, and the significance of differences are analyzed using the log-rank test. Cox proportional hazard regression analysis is used to assess the association between the clinical outcomes and mean sUCR and Δ sUCR. In multivariate analysis, we enter variables using a P value of <0.10 as the selection criterion or considered clinically significant. Hazard ratios (HRs) are presented with 95% CIs. All statistical analysis was performed with the use of SPSS (version 19.0, SPSS, Chicago, USA) and Prism 7.0 (GraphPad Software, San Diego, CA, USA). A two-tailed P value <0.05 was considered to be statistically significant.

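### Mean sUCR, the main exposure, has no averaging rule; if care-driven visit values are weighted equally, clustered illness visits can bias its link with outcome in either direction

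*Combined protocol and SAP*

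**What the plan says.** The design paragraph under Methods states: "This study is a multicenter, retrospective cohort study". Visit timing is therefore a by-product of care, not a protocol schedule.

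Data collection says that treatment-related information is gathered "At baseline and every medical visit". The items listed include "laboratory indexes (serum creatinine, blood urea nitrogen, glycosylated hemoglobin", so both components of sUCR are available at visits.

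Statistics uses the exposure without further definition: "According to mean sUCR and Δ sUCR (fluctuation of sUCR over time, meaning monthly rate of change), patients are divided into four groups". The same two quantities then enter the Cox model. Nothing states which values enter the mean, over what period, with what weights or with what minimum number, and no adjustment for visit frequency is mentioned.

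Study population has one relevant safeguard: "Patients who undergo infection, severe liver disease, malignant tumor, acute heart failure, gastrointestinal hemorrhage, pregnancy are excluded". It does not say whether this is judged at entry or throughout the record.

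The hypothesis closing the Background gives the exposure its meaning: "sUCR can be applied to evaluate of protein intake during the follow-up periods and predict the survival".

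**The concern.** When care decides when blood is drawn, sick patients are sampled more often, and most often while sick. An equal-weight mean counts tests, not time: several tests in a few weeks can carry as much weight as a year of routine visits. Mean sUCR then mixes two things, the patient's habitual level and the intensity of testing during illness.

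If the illness also changes the risk of death or kidney failure, and sUCR moves during it, the mean is associated with outcome even when the habitual level is not. The study wants to read sUCR as a marker of protein intake over follow-up. A hazard ratio produced partly by illness-driven testing would not support that reading, and the planned analysis could not separate the two.

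**Working it through.** The plan has no visit count, sample size, event count or numerical result for this exposure, so there is no figure to reproduce. Every numerical input below is an assumption, except the two-sided 5% level (Statistics).

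**1. Weight of acute values in a plain mean.** With *r* routine and *a* acute values, the acute share is w = a/(r + a), and the mean moves by w × (acute rise).

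| Routine | Acute | Share w | Plain mean if routine sUCR = 15, acute = 25 |
|---|---|---|---|
| 24 | 2 | 2/26 = 8% | 15.8 |
| 12 | 4 | 4/16 = 25% | 17.5 |
| 8 | 4 | 4/12 = 33% | 18.3 |
| 8 | 8 | 8/16 = 50% | 20.0 |
| 4 | 8 | 8/12 = 67% | 21.7 |

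A 14-day episode in two years has a time-weighted mean of 15 + 10 × 14/730 = 15.2. Acute values make up half or more of the plain mean only when acute visits equal or outnumber routine ones.

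**2. One worked patient.** Quarterly visits over 24 months give 9 values. Add one 1-month episode at +2 SD with 4 extra visits.

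- Plain mean: shift 4 × 2/13 = 0.62 SD (acute share 4/13 = 31%).
- Trapezoid time-weighted mean, assuming a 1-month ramp on each side: area 2 × 1 + 2 × (½ × 2 × 1) = 4, and 4/24 = 0.17 SD.
- One value per quarter, 8 quarters: at most 2/8 = 0.25 SD, if an acute value is the one taken.
- True time-average: 2 × 1/24 = 0.08 SD.

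**3. Simulations with no effect of habitual sUCR.** HR is per SD of the mean; % is the share of runs with P < 0.05.

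*Setting A*: 800 patients, 150 runs per row; a shared frailty drives both episodes and death; +2 SD during episodes; values averaged over all follow-up.

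| Acute visits per episode | Average acute share | Plain mean | Time-weighted | Acute values dropped |
|---|---|---|---|---|
| 1 | 5% | 1.03, 6.7% | 1.01, 4.0% | 1.00, 6.0% |
| 3 | 12% | 1.05, 10.7% | 1.02, 6.7% | 1.00, 4.0% |
| 6 | 19% | 1.03, 12.0% | 1.01, 6.7% | 1.00, 9.3% |

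*Setting B*: 1000 patients, 12-month window, quarterly visits, 4 extra visits per episode, +2 SD; 200 runs per row, except 100 in the first.

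| Patients with an episode; later hazard | Plain mean | Time-weighted | Acute values dropped |
|---|---|---|---|
| 25%; ×2 (100 runs) | 1.13, 57% | 1.05, 11% | 1.00, 6% |
| 25%; ×2, about 31% events | 1.12, 53% | 1.05, 18% | 1.00, 5% |
| 25%; ×2, about 17% events | 1.13, 38% | 1.06, 8% | 1.00, 4% |
| 25%; ×1.5 | 1.07, 22% | 1.03, 7% | 1.00, 7% |
| 10% with an episode | 1.06, 18% | 1.03, 7% | 1.00, 7% |
| Control: episode does not affect hazard | near 1.00, 6–7% | near 1.00, 6–7% | near 1.00, 6–7% |

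*Setting C*: 1000 patients, about 200 events, 300 runs, hazard 5% a year, 4 years of follow-up; plain mean only.

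- 12-month window, otherwise as the first row of B: 1.13, 40%.
- 24-month window: 1.09, 25%.
- 24 months, 10% with an episode: 1.04, 9%.
- 24 months, 2 extra visits: 1.05, 10%.
- 24 months, +1 SD episode: 1.04, 9%.
- Episode at −2 SD: HR 0.89, so the bias changes sign.

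Monte Carlo error is about ±3.5 points at 5% with 150 runs and about ±10 points at 57% with 100 runs. The lowest plain-mean figure (6.7%) is therefore not distinguishable from the nominal level; the higher ones are.

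**The case against.** **The plan never says plain mean.** True. Data collection says what is gathered and Statistics says only mean sUCR; equal weighting of every visit is an inference. It is the most natural one, because an unqualified mean beside visit-by-visit collection suggests it. What can be shown is that the exposure is undefined and that its natural reading has a known weakness.

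**Acute values do not dominate.** A reader might infer that they do. They are 31% of the values in the worked patient and 5% to 19% on average in setting A. Excess weight is the supportable description.

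**The exclusion may already cover this.** A reader might assume that it applies only at entry, so that later episodes enter the mean in full. The text does not say so. If it applies across the record, many such episodes go, but patients are then selected on events after baseline. On either reading it acts on patients, not on single values, and covers only the conditions it names.

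**The direction is unknown.** This stands. The documents do not say how sUCR moves in acute illness, so the bias could inflate, mask or reverse an association.

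**The stated object is prognosis, and an association carried by illness can still be prognostic.** This is a fair limit, but not an answer. The hypothesis also takes sUCR to reflect protein intake during follow-up, and that interpretation is what the bias damages.

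**Conclusion.** The concern holds in a limited form. Mean sUCR is the main exposure and has no stated window, weighting or rule for values taken during illness. If all visit values count equally, clustered illness visits get excess weight, and the association with death or kidney outcomes can be biased in either direction.

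The size cannot be fixed from the documents. Under the assumed inputs the false-positive rate ran from about 7% to 57% for the plain mean and from about 4% to 18% for the time-weighted mean, with plain-mean hazard ratios of 1.03 to 1.13 per SD when sUCR rises in the episode. The 57% should not be quoted alone: it comes from a short window, a common episode that doubles the hazard, and only 100 runs. The bias needs three conditions: clustered testing, movement of sUCR in the episode, and an effect of illness on outcome. With the last removed, rates returned to 6–7%.

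This should be corrected before analysis because the remedy is cheap and the exposure is central. It does not show that any result will be false.

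**What to change.** In Statistics, define mean sUCR over a stated exposure window as either a time-weighted average or the mean of one value per calendar quarter, with the rule for choosing that value. In Study population, state whether the exclusion of acute conditions applies at entry only.

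Report two sensitivity analyses: the plain mean of all visit values and, where episode dates can be found in the records, the mean without values taken during the named acute conditions. The second matters because time-weighting reduces the bias without removing it (up to 18% significant in the runs above), whereas dropping acute values brought the HR to about 1.00. It is not proposed as the main definition because Data collection lists complications but does not clearly provide for episode dates.

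The cost is a little more programming and some flagging of records. In the second sensitivity analysis some patients lose a few values. No new measurements are needed.

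### One survival-framed censoring rule serves both outcomes, so time without a creatinine test can count as free of the kidney event

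*Combined protocol and SAP*

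**What the plan says.** The Outcomes section has one sentence on follow-up and censoring: "Patients are followed for survival until they reach the end of the study, whichever happen first, or are censored because they lose contact", with a further reason, "or the follow-up interval is less than one month". It is framed around survival. The text goes straight on to the outcomes: "The outcomes are all-cause death, a composite of end-stage kidney disease", defined by "dialysis, transplantation, or a sustained estimated GFR of <15 ml per minute" (indexed to 1.73 m²). The remaining kidney criterion is "increasing by 50% of the serum creatinine level from baseline".

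The Data collection section says "At baseline and every medical visit, therapeutic relevant information will be collected" and lists serum creatinine among the laboratory indexes. It gives no interval between visits or tests. Under Methods, "This study is a multicenter, retrospective cohort study".

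The Statistics section forms groups from mean sUCR and its monthly rate of change ("patients are divided into four groups") and applies Kaplan-Meier, log-rank and Cox methods. It adds no censoring date for the kidney outcome, no maximum gap between tests and no interval-censored method.

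**The concern.** Contact with a patient shows that the patient is alive, so censoring death at study end or loss of contact is sound. Contact does not show that creatinine has not risen by half. If the same date closes the kidney outcome, all time between the last creatinine and that date enters the risk set, although no creatinine-defined event could be recorded in it.

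There are two consequences. Absolute kidney-free survival is too high whatever the pattern of testing. If the untested tail is longer in one sUCR group, that group's kidney hazard is lowered by more and the comparison is distorted. The plan's stated object is the prognostic value of sUCR for progression of DKD, so the kidney outcome is central. The exposure is also calculated from blood tests at visits, so a link between group and amount of testing is plausible. The documents do not show that one exists.

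**Working it through.** The documents give no sample size, event count, event rate or effect size, so there is no planned figure to reproduce. The text settles what the rule is; the arithmetic shows how large the effect could be.

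**Which outcomes need a test**

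| Outcome | Visible without a creatinine test? |
|---|---|
| Death | Yes |
| Dialysis, transplantation | Yes |
| Sustained eGFR below 15 | No; needs repeated tests |
| 50% creatinine rise | No |

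**Assumed inputs (none is in the documents).** Constant kidney hazard λ = 0.08 per year in both groups, so the true ratio is 1.00. Contact time C is uniform on 2 to 7 years. The last creatinine falls g years before the end of contact.

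**Censoring at end of contact, every event test-detected.** Let M = E[exp(−λC)] = (e^−0.16 − e^−0.56)/(0.08 × 5) = (0.8521 − 0.5712)/0.4 = 0.7023.

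- Events per patient: E = 1 − e^(λg)·M.
- Person-years per patient: P = E/λ + g·e^(λg)·M. The second term is the untested tail.
- Example, g = 1.5: e^0.12 × 0.7023 = 0.7919; E = 0.2081; P = 2.601 + 1.188 = 3.789; rate 0.0549.

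**With 30% of events known without a test (assumed).** Those patients have E = 1 − M = 0.2977 and P = 0.2977/0.08 = 3.721. The group's E and P are 0.7 and 0.3 weighted sums.

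| g (years) | E | P | Rate | Ratio to g = 0.5 | Rate, 30% known | Ratio, 30% known |
|---|---|---|---|---|---|---|
| 0.5 | 0.2690 | 3.728 | 0.0722 | 1.00 | 0.0745 | 1.00 |
| 0.75 | 0.2542 | 3.737 | 0.0680 | 0.94 | 0.0716 | 0.96 |
| 1.0 | 0.2392 | 3.750 | 0.0638 | 0.88 | 0.0686 | 0.92 |
| 1.5 | 0.2081 | 3.789 | 0.0549 | 0.76 | 0.0623 | 0.84 |

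Simulation of the same set-up agrees, with 0.83 to 0.84 in the last cell. Even with equal gaps the rate is wrong: at g = 0.5 it is 0.0722 against a true 0.08, which is 10% too low.

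**Censoring at the last creatinine.** The tail term drops out, so P = E/λ and the rate is 0.08 for every g. The ratio is 1.00.

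**Counting late dialysis or transplantation while censoring everyone else at the last test (30% share).** Events are as in the 30% case. Person-years are 0.7·E/λ + 0.3·(3.721 − g·M), where E is the test-detected value.

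- g = 0.5: 0.2776/3.365 = 0.0825.
- g = 1.5: 0.2350/2.621 = 0.0896.
- Ratio 1.09: the bias is reversed.

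**A second assumed model: patients stop testing while contact continues.** Five years of contact, 3-monthly tests, hazards of 0.05 to 0.20 per year. Stopping at 20% v 5% per year gives 0.68 to 0.70 under end-of-contact censoring, or 0.78 to 0.80 if 30% of events are known without a test. Yearly v 3-monthly testing with no stopping gives only 0.93 to 0.98. When spacing differs, censoring at the last test still leaves 0.93 to 0.99, because detection is delayed.

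**Chance of a false finding.** With an assumed 200 events in two equal groups and a spurious ratio of 0.8, √(200/4) × |ln 0.8| = 1.578, and Φ(1.578 − 1.96) = 0.35 at the two-sided 5% level.

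**The case against.** The strongest reply is that this is a gap in wording. The censoring sentence speaks of survival and does not say in terms that its date closes the kidney outcome. Loss of contact is undefined, and the only contact described is the medical visit, with creatinine among the data listed. If contact means a visit with bloods, a patient who stops attending is censored near the last creatinine. Grouping by sUCR also requires creatinine values, so analysed patients have been tested.

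Part of this stands. Under that reading the problem shrinks for patients lost to contact. It remains for patients carried to the end of the study without a recent test. Having the values needed for sUCR does not rule out a long gap at the end. No other rule is written for the kidney outcome, so an analyst following the plan would use this one.

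Three further points stand. Dialysis and transplantation dilute the bias. The gap lengths are assumed, and small differences in gap give small bias. Censoring at the last creatinine has its own assumptions and costs.

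A reader might infer that the plan favours a particular sUCR group, or that its hazard ratio is biased by some known amount. The documents support neither: they do not report testing by group, and they do not describe long untested periods in patients still in contact.

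**Conclusion.** The point holds in a conditional form. The one stated censoring rule suits death but not the two creatinine-defined components. Wherever a patient is carried past the last creatinine, kidney-free survival is overstated. The between-group comparison is biased only if the gap from last test to end of contact differs among the sUCR groups, and then in favour of the less-tested group.

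The size in this cohort is unknown. Under the main assumed model the false ratio lies between 0.94 and 0.76 for gaps of 0.5 v 0.75 to 0.5 v 1.5 years, or between 0.96 and about 0.84 if 30% of events need no test. It is 1.00 with equal gaps. These figures rest on a constant 8% yearly hazard, contact of 2 to 7 years and testing unrelated to kidney risk. The correction is worth making because it relies on creatinine data the plan already collects.

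**What to change.** State a censoring date for each outcome:

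- **Death:** the last date known alive, or the end of the study.
- **Kidney composite:** the last serum creatinine date, counting dialysis and transplantation only up to that date. Adding later ones while everyone else is censored at the last test reverses the bias, as shown above.
- **Sensitivity analysis:** dialysis or transplantation alone, followed to the last date that status is known.

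Define loss of contact. Report, by sUCR group, creatinine tests per year and the gap from last test to end of contact; that table would show whether the comparison is affected in this cohort.

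The cost is a few sentences, one more date variable and one table. The kidney analysis loses some person-time, and some late dialysis or transplant events leave the main composite. The method assumes that stopping tests is unrelated to kidney risk. A small bias from unequal test spacing remains; removing it would need a maximum-gap rule or an interval-censored analysis.

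### Serum creatinine is the sUCR denominator and also defines limbs of the kidney outcome; with no exposure window set, the kidney hazard ratio, mainly for ΔsUCR, can be distorted in either direction

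*Combined protocol and SAP*

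**What the plan says.** All references are to the combined protocol and SAP.

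- **Exposure.** Background introduces the marker by citing work in which "serum urea nitrogen to creatinine ratio (sUCR) correlated closely with protein intake". Creatinine is its denominator. The hypothesis that closes Background is that "we hypothesize sUCR can be applied to evaluate of protein intake during the follow-up periods and predict the survival in patients with DKD".
- **Aim.** Object: "To evaluate the prognostic value of sUCR in the progression of DKD".
- **Measurement times.** Data collection: "At baseline and every medical visit, therapeutic relevant information will be collected". Serum creatinine and blood urea nitrogen are among the laboratory items.
- **Outcome.** Outcomes names all-cause death, and kidney failure by dialysis, transplantation or a sustained eGFR below 15, "or increasing by 50% of the serum creatinine level from baseline". eGFR comes from CKD-EPI. The punctuation leaves it unclear whether death stands alone or belongs to the composite.
- **Analysis.** Statistics forms four groups from mean sUCR and ΔsUCR (its change per month) and relates both to the outcomes by Kaplan-Meier, log-rank and Cox methods. It gives no start or end for the values used, no cut at the event, no lag or landmark, no time-dependent covariate, and no formula for ΔsUCR. The only time rule, in Outcomes, concerns censoring when follow-up is under one month.

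**The concern.** The exposure and part of the outcome are computed from one creatinine series. If all follow-up values are used, a patient's group is partly decided by readings taken as the event occurs. With no effect of protein intake at all, two mechanisms can then link ΔsUCR to the kidney outcome:

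- **(a) Unequal tracking.** If urea does not rise in proportion to creatinine, sUCR drifts as kidney function falls.
- **(b) Shared creatinine error.** If urea does rise in proportion, a chance-high creatinine can still trigger the 50% limb while lowering sUCR at that visit, and a chance-low baseline starts sUCR high while making the 50% rise easier to reach. This requires that urea and creatinine errors at a visit are not strongly correlated.

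Two readings of the result are at stake. A predictor that includes event-time values is not a clean measure of prognostic value for the kidney outcome. And sUCR is also to be read as protein intake: Background states "The lower the baseline dietary protein intake (DPI), the slower the progression toward ESRD". An artefact that ties falling sUCR to worse outcome runs against that expectation and could hide or reverse a true association. One in the other direction could imitate it.

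**Working it through.** **No figure to reproduce.** The plan states no sample size, event count or effect size. The structure comes from the text; every simulation input below is assumed.

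**Step 1: arithmetic.** Let urea change as creatinine to the power e (elasticity e). When creatinine is multiplied by 1.5, sUCR changes by 1.5^(e−1) − 1:

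- e = 0: 1/1.5 − 1 = −33.3%
- e = 0.5: −18.4%
- e = 0.75: −9.6%
- e = 1: 0%
- e = 1.25: +10.7%

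One value that is 33.3% low moves a mean of 5 values by −33.3/5 = −6.7% and a mean of 13 by −33.3/13 = −2.6%. A slope is more exposed, because the event value lies at the end of the series.

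**Step 2: null simulation (intake unrelated to outcome).** Assumed: 600 patients; baseline eGFR at least 15 (in line with CKD stages 1-4 in Study population); visits every 3 months; follow-up 24 to 60 months; log-creatinine slope mean 0.06 per year, SD 0.12; visit error SD 0.08 (log creatinine) and 0.12 (log urea), independent unless stated; log-intake SD 0.2 between patients, with drift SD 0.05 per year. Endpoint: creatinine at least 1.5 times baseline, or two consecutive eGFR values below 15, unless stated. ΔsUCR is a least-squares slope unless stated. Hazard ratios compare below with above median; the true value is 1.

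| Setting | e=0.5 | e=0.75 | e=1 | e=1.25 |
|---|---|---|---|---|
| ΔsUCR, all follow-up | 5.3 | 2.8 | 1.4 | 0.75 |
| same, error correlation 0.67 | 4.8 | 2.3 | 1.0 | 0.44 |
| same, half the slope SD | 3.4 | 2.3 | 1.5 | 1.04 |
| same, ΔsUCR as last minus first over time | 6.2 | 3.5 | 2.1 | 1.16 |
| Mean sUCR, all follow-up, kidney composite with assumed dialysis/transplantation | 1.6 | 1.4 | 1.0 | 0.74 |
| ΔsUCR, all follow-up, death alone, unrelated to kidney function | 1.05 | 1.01 | 1.02 | 1.00 |
| ΔsUCR, 12-month landmark | 2.1 | 1.5 | 1.1 | 0.79 |
| same, half the slope SD | 1.8 | 1.5 | 1.3 | 1.10 |

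Repeat runs of the first row ranged over 5.3 to 5.6, 2.8 to 2.9, 1.4, and 0.72 to 0.75.

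**Step 3: can a true association be masked or reversed?** A simpler simulation (600 patients, 3-monthly visits to 48 months, log-sUCR visit SD 0.15) changed only the event-visit value: creatinine ×1.5, urea ×f. A truly rising sUCR raised the hazard 1.5-fold. The estimate for high versus low ΔsUCR was 0.23, 0.52, 1.19 and 2.84 at f = 1, 1.25, 1.5 and 1.8. Since e = ln f / ln 1.5, these correspond to e = 0, 0.55, 1 and 1.45. The first two are reversals; the estimate crosses 1 (masking) between f = 1.25 and 1.5; the last is an exaggeration. This simulation has no shared creatinine error and no decline before the event, so it says nothing about mechanism (b) or about how well a window works.

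**Step 4: partial remedies.** Omitting only the event visit takes the ΔsUCR hazard ratio from 1.44 to 0.97 at e = 1, but from 0.75 to 0.53 at e = 1.25, further from 1. Within the landmark, omitting the baseline visit takes 2.06, 1.49, 1.09, 0.81 to 1.51, 1.20, 0.97, 0.77: better in the first three settings, slightly worse in the last. Adding baseline eGFR leaves the landmark values almost unchanged (2.03, 1.48, 1.11, 0.80 become 2.03, 1.48, 1.10, 0.80).

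**The case against.** **A prognostic marker may carry kidney-function information.** True, and no fault in itself. What remains is the timing of the measurements, and the reading of sUCR as protein intake.

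**The plan is silent; the analysts might use only early values.** They might. A reader might infer that the planned Cox model cannot estimate prognostic value at all. The documents do not support that: no window is stated, but neither is it stated that event-time values will be used. The risk also concerns the kidney outcome. All-cause death does not share creatinine by definition, and simulated death unrelated to kidney function gave hazard ratios near 1.

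**Urea and creatinine errors may move together.** This limits mechanism (b). A reader might infer that bias persists whenever urea rises in step with creatinine; at an assumed error correlation of 0.67 the hazard ratio at e = 1 is 1.0. Mechanism (a) is untouched: 4.8 at e = 0.5 and 0.44 at e = 1.25.

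**The covariate rule in Statistics could already admit baseline eGFR.** It could, but that barely moves the ΔsUCR hazard ratio.

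**The window is imperfect.** This stands. It does not remove decline before the event, and at half the slope SD and e = 1.25 it does not shrink the artefact (1.04 against 1.10).

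**Conclusion.** The concern holds for the kidney outcome, mainly for ΔsUCR, and should be fixed before analysis. The shared creatinine term and the absent window are in the text, with one qualification: that the eGFR limb uses creatinine is very probable rather than stated.

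The planned hazard ratio can show, mask or reverse an association (a) whenever urea does not rise in proportion to creatinine, and (b) under proportional urea, only to the extent that the visit errors are not strongly correlated. Over the elasticities tried, the null ΔsUCR hazard ratio ran from about 5.3 to 0.75 with independent errors and from 4.8 to 0.44 with error correlation 0.67. Mean sUCR was affected less.

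These sizes rest wholly on assumed inputs, including the least-squares definition of ΔsUCR. They show the mechanism and are not estimates of this study's bias. A reader might infer a known direction; the documents give neither the urea-creatinine relation nor the error structure, so none can be claimed.

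**What to change.** Add to Statistics:

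1. *Mean sUCR and ΔsUCR (least-squares slope per month) are computed from visits in a fixed window, for example the first 12 months. Follow-up for outcomes starts at the end of the window; patients with an event or censoring in the window are excluded and counted. As a sensitivity analysis, ΔsUCR is recomputed without the baseline visit, whose creatinine is the reference for the 50% rise.*
2. *All-cause death and dialysis/transplantation are each reported separately from the creatinine-defined limbs.* This also settles the status of death left open in Outcomes. It removes the shared measurement but not confounding by kidney decline.
3. *Baseline eGFR is included in every Cox model.*
4. Because the window leaves some artefact: *ΔsUCR results for the kidney outcome are described as prognostic and not as evidence about protein intake.*

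Two additions may tempt but are not advised. Adjusting for the eGFR slope within the window overshot under the null (0.81, 0.67, 0.56, 0.47), ending further from 1 than no adjustment at e = 1 and 1.25. Making the dietary reading depend on a confidence interval from urine urea is also unattractive: Data collection does list "24-hour urinary albumin, 24-hour urine urea nitrogen, etc", but Background says the urine method cannot be "generalized due to its complexity and uncertainty", and the values may be sparse in a retrospective cohort.

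The cost is wording and a few extra models, with no new measurements. Early events are lost (in the simulation about 16 of 216, or 7.4%; at half the slope SD 5 of 165, or 3.0%). The exposure narrows from follow-up as a whole to the window, the slope without baseline is noisier, and separate outcomes have wider intervals (about 42 deaths against about 200 kidney events in the simulated landmark sets).
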